### 6.6. Treatment Compliance

Patient compliance with study drug will be monitored by capsule count.

#### 7. STUDY CALENDAR

All procedures and evaluations may be performed within  $\pm$  3 calendar days of that specified in the protocol to accommodate patient convenience and scheduling. Patient consent must be obtained prior to any study-specific procedures.

Table 5 Study Flow Chart

Procedure	Pre- Study c	Cycle 1 (Day 1±3 d)	Cycle 1 (Day 8 ± 3d)	Cycle 1 (Day 15 ±3d)	Cycle 2 and subsequent cycles (Day 1 ± 3d)	Post-treatment follow-up i
Sapacitabine administration		X f			X	
Informed consent	X					
Medical history	X					
Concomitant meds	X	X g	X	X	X	X
Capsule count					X	
Physical exam in clinic (including vital signs and performance status)	X	Xg	X	Х	X g	X
Height	X					
Weight	X				X	X
CBCa	X	X g	X	X	X	X
Chemistry panel b	Х	X g	X		X	X
INR	X					
Transfusion requirements	X d		X	X	X	X
Number of hospitalized days	Xe		Х	Х	Х	X
Bone marrow aspirate and/or biopsy	Х				X h	
Bone marrow cytogenetics	X e					
Pulmonary function test of FEV1 and DLco	X e					
ECG	X		Х	X		X
Adverse events assessment			X	X	X	X
Chest x-ray (PA and Lateral)	X					

a: Differential of WBC will be done if WBC ≥ 300/µL

CYCLACEL LTD CONFIDENTIAL 29 of 56

b: Albumin, alkaline phosphatase, total bilirubin, bicarbonate, blood urea nitrogen, calcium, chloride, creatinine, glucose, lactic dehydrogenase, phosphorus, potassium, total protein, SGPT[ALT], SGOP (AST), sodium, uric acid

c: Within 2 weeks of the first dose of study drug except bone marrow cytogenetics which will be performed within 3 months (all patients) and pulmonary function test of forced expiratory volume in 1 second (FEV1) and lung diffusion capacity of carbon monoxide (DLco) which will be performed within 28 days prior to the first dose of the study drug as clinically indicated (Part 2 and 3 only); informed consent form may be obtained > 2 weeks prior to the first dose of drug but must be obtained prior to conducting any study-specific procedures

d: Transfusion requirements during the 8 weeks immediately prior to the first dose of study drug

e: Number of hospitalized days during the 8 weeks immediately prior to the first dose of study drug

f: The first dose of study drug must be administered within 7 days of randomization; sapacitabine may be dispensed at pre-study visit if the pre-study visit is within 7 days of the first dose of the study drug

g: These evaluations on Day 1 Cycle 1 may not need to be performed if the same evaluations performed during Pre-Study period are within 7 days of the first dose of the study drug; physical exam in clinic may be waived every 1-2 cycles at the investigator's discretion after cycle 6.

h: To be performed prior to the start of cycle 2 on patients who have >5% blasts in bone marrow, i.e., during Day -21-28 of Cycle 1 which may be delayed up to Day 35 for recovery of blood counts; as clinically indicated after subsequent cycles e.g., at the time when blood counts have recovered or worsened.

i: Within 28 days after the last dose of study drug if possible or prior to the initiation of new anticancer treatment, whichever comes first.

#### 8. SAFETY ASSESSMENT

Safety parameters include early death rate and 30-day mortality rate as defined in section 11.2, adverse events, serious adverse events (SAEs), and overall survival.

### 8.1. Adverse Event Intensity and Relationship to Study Drug

An adverse event (AE) is any unfavorable and unintended sign (including an abnormal laboratory finding, for example), symptom, or disease temporally associated with the use of a medicinal product, whether or not it is considered related to treatment with the medicinal product. This includes the worsening of a pre-existing condition or the increase in frequency of a pre-existing condition. Treatment-emergent adverse events are defined as adverse events that occur after study drug administration begins through 28 days after the last dose of study drug or until the beginning of a new anticancer therapy, whichever comes first. This trial will record treatment-emergent adverse events. Adverse events that occur after the last dose of study drug, regardless of time frame, should also be reported if a casual relationship to the study drug is suspected. The NCI Common Terminology for Adverse Events (CTCAE) version 3.0 will be used to assess the severity of adverse events. Toxicities that cannot be graded using the CTCAE will be graded as grade 1 (asymptomatic), grade 2 (symptomatic but not interfering significantly with function), grade 3 (causing significant interference with function), or grade 4 (life-threatening). For this study, transfusion-dependent anemia and thrombocytopenia defined as requiring transfusion at least once per month will have a severity of grade 4.

An AE is considered serious if it meets any of the serious criteria listed in Section 8.2. To ensure no confusion or misunderstanding of the difference between the terms "serious" and "severe", which are not synonymous, the following clarification is provided:

• The term "severe" is often used to describe the intensity (severity) of a specific event (as in mild, moderate, or severe myocardial infarction); the event itself, however, may be of relatively minor medical significance (such as severe headache). This is not the same as "serious", which is based on patient/event outcome or action criteria usually associated with events that pose a threat to a patient's life or functioning. Seriousness (not severity) serves as a guide for defining regulatory reporting obligations.

All AEs will be evaluated by the Investigator for potential relationship to the study drug in the following categories:

- Definite The AE *is clearly related* to the study treatment.
- Probable The AE *is likely related* to the study treatment.
- Possible The AE may be related to the study treatment.
- Unlikely The AE is doubtfully related to the study treatment.
- Unrelated The AE *is clearly NOT related* to the study treatment.

All drug-related AEs and SAEs must be followed until resolution or until no further improvement is expected or until the initiation of a new anticancer treatment.

If a male patient's partner becomes pregnant while on study, the investigator will report the pregnancy to Theradex® within 24 hours after the first knowledge of the pregnancy via telephone or fax. The investigator will make every effort to obtain permission to follow the outcome of the pregnancy and report the condition of the fetus and newborn to Theradex® when it becomes available.

Safety Desk
Theradex®
[name]
[name]
[contact]
[contact]

### 8.2. Serious Adverse Event Reporting

A serious adverse event is defined as an untoward (unfavorable) medical occurrence that at any dose:

- Results in death
- Is life-threatening. The term "life-threatening" refers to an event in which the patient was at risk of death at the time of the event; it does not refer to an event which hypothetically might have caused death if it were more severe.
- Requires inpatient hospitalization or prolongation of existing hospitalization
- Results in persistent or significant disability/incapacity
- Is a congenital anomaly/birth defect
- Jeopardizes the subject/patient and may require medical or surgical intervention to prevent one of the outcomes listed above

Important medical events that do not result in death, are not life-threatening, or do not require hospitalization could be considered SAEs when, based upon appropriate medical judgment, they jeopardize the subject, or require medical or surgical intervention to prevent any of the outcomes listed above. Examples of such medical events include allergic bronchospasm requiring intensive treatment in an emergency room or at home, blood dyscrasias or convulsions that do not require hospitalization, or development of drug dependency or drug abuse.

Any SAE or death that occurs after study drug administration through 28 days from the last dose of study drug or until the initiation of a new anticancer therapy, whichever comes first, must be reported to Theradex® immediately via telephone or FAX within 24 hours of the first

knowledge of the occurrence of the event. In addition, any SAE and death that occurs while a patient is not receiving the study drug but remains on study, must also be reported to Theradex as described above.

- For this study, myelosuppression and its associated complications due to underlying leukemia and/or anti-leukemia therapy are expected events during therapy. Hospitalizations for the treatment of the following events that are known to be associated with myelosuppression from leukemia and/or study drug are not required to be reported to Theradex® but still need to be captured as SAEs on the case report form :
  - o Fatigue, weakness and/or shortness of breath associated with anemia
  - o Febrile neutropenia
  - Mucosal bleeding due to thrombocytopenia e.g., epistaxis, gastrointestinal bleeding
  - o Bacteremia, sepsis, pneumonia, cellulitis, neutropenic colitis
- Death due to progression of AML and its associated complications are not required to be reported to Theradex® but still need to be captured as SAEs on the case report form^5.

Any SAE occurring at any other time after completion of the study must also be promptly reported to Theradex®, if a causal relationship to the study drug is suspected. If an SAE is initially reported via telephone, this must be followed-up with a written report via FAX within 24 hours of the telephone report. During both business and non-business hours, the telephone number listed below should be used to notify Theradex®.

Safety Desk
Theradex®
[name]
[name]
[contact]

[contact]

The investigator is required to complete the SAE report form provided by Cyclacel. Sufficient details must be provided to allow for a complete medical assessment of the SAE and independent determination of possible causality. The investigator is obliged to pursue and provide additional information as requested by the Cyclacel medical monitor or its designee. More details on SAE reporting and the SAE reporting form can be found in the Operations Manual.

It is the responsibility of the investigator to promptly notify the IRB or EC of SAEs and/or adverse drug reactions according to institutional guidelines and applicable local laws and regulations.

#### 9. EFFICACY ASSESSMENT

The primary efficacy endpoint of Part 1 of this study is 1-year survival, i.e., the proportion of patients who are alive at 1-year measured from the date of the randomization. Secondary efficacy endpoints are the rate of CR, CRp, PR or CRi or hematological improvement and their corresponding durations, transfusion requirements and number of hospitalized days. The primary efficacy endpoints of Part 2 of this study are the rate of clinical benefit response (CR, CRp, PR, or major HI) and the rate of complete response (CR or CRp). Secondary efficacy endpoints are response durations, transfusion requirements, number of hospitalized days, and overall survival. The primary efficacy endpoint of Part 3 and 4 of this study is 1-year survival rate. Secondary efficacy endpoints are the rate of clinical benefit response (CR, CRp, PR, major HI or SD) and their corresponding durations, transfusion requirements, number of hospitalized days and overall survival.

The tissue samples supporting the diagnosis of AML or MDS, and the responses to sapacitabine may be submitted for central review.

Table 6 Response Criteria

Passansa Description					
Response	Description				
Complete Remission (CR) 	Normalization of peripheral neutrophils to ≥1000 /µL, platelet to ≥100,000/µL within 2 weeks of bone marrow biopsy/aspirate, and bone marrow to ≤5 % blasts; independent of transfusions*; and no extramedullary leukemia.				
Complete remission with incomplete platelet count recovery (CRp) 	Normalization of bone marrow to $\leq$ 5% blasts; peripheral neutrophils $\geq$ 1000 /µl, platelet $<$ 100,000 /µL within 2 weeks of bone marrow biopsy/aspirate; independent of transfusions*; and no extramedullary leukemia.				
Complete remission with incomplete blood count recovery (CRi) 8	Normalization of bone marrow to $\leq$ 5% blasts; peripheral neutrophils $<1000~/\mu$ L, platelet $<100,000/\mu$ L within 2 weeks of bone marrow biopsy/aspirate; independent of transfusions *; and no extramedullary leukemia.				
Partial Remission (PR) 8	Normalization of peripheral neutrophils to $\geq 1000 \ / \mu L$ , platelet to $\geq 100,000/\mu L$ within 2 weeks of bone marrow biopsy/aspirate, $\geq 50\%$ decrease in bone marrow blasts over pretreatment but still >5%; independent of transfusions * .				
Hematological improvement (HI) 9	Major response:				
	(1) For patients with pretreatment hemoglobin < 11 g/dL, >2g/dL increase in hemoglobin; for RBC transfusion - dependent patients, transfusion - independence*				
	(2) For patients with a pretreatment platelet count <100,000/mm³, an absolute increase of ≥30,000/mm³; for platelet transfusion-dependent patients, stabilization of platelet counts and platelet transfusion independence*.				
	(3) For patients with absolute neutrophil count (ANC) $< 1,500/$ mm  before therapy, $\ge 100\%$ increase, or an absolute increase $> 500/$ mm  , whichever is greater.				
	Minor response:				
	(1) For patients with pretreatment hemoglobin < 11 g/dL, 1-2 g/dl increase in hemoglobin; for RBC transfusion – dependent patients, 50% decrease in transfusion requirements.				
	(2) Platelet response: for patients with a pretreatment platelet count $<100,000/\text{mm}^3, \ge 50\%$ increase in platelet count with a net increase $>10,000/\text{mm}^3$ but $<30,000/\text{mm}^3$ .				
	(3) For patients with absolute neutrophil count (ANC) $< 1,500/$ mm  before therapy, $\ge 100\%$ increase, but absolute increase $< 500/$ mm  .				
Stable disease (SD)**	Failure to achieve at least HI, but no evidence of clinically significant progression for > 16 weeks.				

\*independent of transfusions or transfusion –dependence refer to no packed red blood cell transfusion for 2 weeks and no platelet transfusion for 1 week .

Transfusion requirements for each patient are defined as the number of weeks during which at least one transfusion for red blood cells (RBCs) or platelets is administered and the mean number of units of RBC and platelet transfusions administered per month.

CYCLACEL LTD CONFIDENTIAL 34 of 56

\*\* for Part 2, 3 and 4 of the study only

Clinical benefit is defined as the achievement of CR, CRp, PR, major HI or SD. The duration of clinical benefit is measured from the earliest time when the patient achieved CR, CRp, PR or major HI to the first date when the major HI is lost; if the patient only achieved SD, the duration of clinical benefit is measured from the date of randomization or registration to the first date when clinically significant progression of disease is observed.

The duration of CR, CRp, PR or CRi or hematological improvement is measured from the time when response criteria are first met until the first date that recurrent or progressive disease is documented. To avoid premature discontinuation of patients who have had a temporary flare of the disease due to treatment interruptions, dose reductions, acute infection or other plausible explanations, a second assessment should be performed in these patients to confirm the recurrence or progression of disease.

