#### 11.1.1. Screening Design

In the screening phase, a Bayesian continuous futility monitoring rule will be implemented based on the rate of CR plus CRi in each of the 3 arms of the AML stratum, respectively. An arm will be stopped if Prob (CR+CRi > 25% | data) < 0.05. The above stopping rule suggests that, given the data obtained from patients who have already been evaluated in an arm, if there is less than a 5% chance that the rate of CR+CRi is greater than 25% we will terminate the arm. This decision rule generates the following stopping boundaries, assuming a beta(1,1) prior distribution for the response (CR+CRi) rate in each arm. Stop an arm i if [ # of pts with CR or CRi in arm i / # of pts evaluated in arm i ]  $\leq$  0/10, 1/17, where i = 1, 2, or 3. The operating characteristics of this rule are shown in Table 8.

Table 8 Operating Characteristics of Futility Monitoring - Maximum 20 AML Patients

		Sample Size		
Rate of CR or CRi	Probability of stopping	P 25	P 50	P 75
0.05	0.822	10	10	17
0.10	0.54	10	17	20
0.15	0.313	17	20	20
0.20	0.165	20	20	20
0.25	0.082	20	20	20
0.30	0.039	20	20	20

After treating up to 10 evaluable AML patients defined as patients who have completed at least 1 cycle of treatment at each dosing schedule

- If no CR or CRi is observed, declare the treatment insufficiently active and no more AML patient will be treated with this dose regimen
- If at least one CR or CRi is observed, add AML patients to reach a total of 17 patients and
  - o If less than two CR plus CRi are observed, declare the treatment insufficiently active
  - o If at least two CR and CRi are observed, add AML patients to reach a maximum of 20 patients

For both AML and MDS patients, there is an early stopping rule for excessive toxicity. A dosing schedule will be declared to have excessive toxicity and no more patients will be treated with this dose regimen if among the first 10 patients treated with this dose regiment in either the AML or MDS stratum, there are > 2 patients experienced serious adverse events (excluding simple complications associated with myelosuppression such as neutropenic fever without shock or its complications from gram-negative bacteremia, anemia or mucosal bleeding, *e.g.*, epistaxis, due to thrombocytopenia easily controlled by transfusion) that are considered by investigator to be definitely, probably or possibly related to the study drug during the first two treatment cycles.

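### Table 6 places marrow remission with neutrophils below 1000 and platelets of at least 100,000 in none of CR, CRp, CRi or PR, so the Part 1 AML rules on CR plus CRi count it as non-response

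*Combined protocol and SAP*

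**What the plan says.** Section 9, Table 6 sets the response categories. The rows that matter here are:

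- CR: "Normalization of peripheral neutrophils to ≥1000 /µL, platelet to ≥100,000/µL within 2 weeks of bone marrow biopsy/aspirate, and bone marrow to ≤5 % blasts".
- "Complete remission with incomplete platelet count recovery (CRp": blasts ≤5%, neutrophils ≥1000 and platelets <100,000.
- "Complete remission with incomplete blood count recovery (CRi": blasts ≤5%, with "peripheral neutrophils $<1000~/\mu$ L, platelet $<100,000/\mu$ L within 2 weeks of bone marrow biopsy/aspirate".
- PR: both counts recovered and a blast reduction of at least half, but "decrease in bone marrow blasts over pretreatment but still >5%; independent of transfusions".
- Major HI by platelets: "For patients with a pretreatment platelet count <100,000/mm³, an absolute increase of ≥30,000/mm³". This row sets no blast or neutrophil condition.
- SD, in Parts 2, 3 and 4 only: "Failure to achieve at least HI, but no evidence of clinically significant progression for > 16 weeks".

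Section 11.1.1 uses CR and CRi to monitor each Part 1 AML arm: "Stop an arm i if [ # of pts with CR or CRi in arm i / # of pts evaluated in arm i" is at or below 0/10 or 1/17. The same section allows more AML patients once a schedule has four or more CR and CRi with a 30-day death rate of 20% or less. Section 11.4 analyses added patients separately where a schedule has reached 20% CR/CRi, and reports the CRi rate with a 95% confidence interval.

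**The concern.** Among patients with blasts ≤5% there are four combinations of neutrophils (below 1000, or not) and platelets (below 100,000, or not). Table 6 names three of them. The missing one is low neutrophils with recovered platelets.

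The resulting order is illogical. Neutrophils of 800 with platelets of 60,000 is CRi; neutrophils of 800 with platelets of 150,000 is not, although one count is better and the other is the same.

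Where CRi counts towards a decision, the error runs one way: it can only lower the CR plus CRi count and make stopping more likely. The margins are single patients. One of 17 stops an arm and 2 of 17 does not; 3 of 20 falls short of the expansion trigger and 4 of 20 meets its response part. Isolated neutropenia is plausible with this drug, since Sections 1.4 and 1.6 list neutropenia and its complications among the toxicities. Section 3.7 lets the investigator's CRF assessment serve as source data and Section 9 makes central review optional, so nothing guarantees that about 25 sites would resolve the gap in the same way.

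**Working it through.** **Classification.** The CR, CRp, CRi and PR rows are applied as written. The transfusion, timing and extramedullary conditions are assumed met where they apply, and for PR also the required fall in blasts.

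| Blasts | Neutrophils | Platelets | Category |
|---|---|---|---|
| ≤5% | ≥1000 | ≥100,000 | CR |
| ≤5% | ≥1000 | <100,000 | CRp |
| ≤5% | <1000 | <100,000 | CRi |
| ≤5% | <1000 | ≥100,000 | none of CR, CRp, CRi, PR |
| >5% | ≥1000 | ≥100,000 | PR |

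**The plan's boundaries.** Inputs from Section 11.1.1: a beta(1,1) prior, a 25% threshold and a 0.05 cut-off. After x responses in n patients the posterior is beta(1+x, 1+n−x). Then P(rate >25%) is:

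- 0/9: 0.75^10 = 0.056; 0/10: 0.75^11 = 0.042.
- 1/16: 0.0501; 1/17: 0.0395.

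The first crossings of 0.05 are at 0/10 and 1/17, as the plan states.

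**The plan's Table 8.** An arm stops with no response in 10, or with one response in the first 10 and none in the next 7:

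P(stop) = (1−p)^10 + 10p(1−p)^9 × (1−p)^7

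- p = 0.25: 0.0563 + 0.0251 = 0.081 (Table 8: 0.082).
- p = 0.20: 0.1074 + 0.0563 = 0.164 (Table 8: 0.165).
- p = 0.05, 0.10, 0.15 and 0.30: 0.819, 0.534, 0.308 and 0.038 (Table 8: 0.822, 0.54, 0.313 and 0.039).

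Table 8 is reproduced to within one percentage point.

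**Effect of the gap.** Let g be the share of true CR plus CRi responders who fall in the gap. The documents do not give g, so every value below is an assumption. The rate the rule sees is p(1−g). At a true rate of 25%:

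| g | Rate seen | P(stop) | P(at least 4 of 20), ignoring stopping |
|---|---|---|---|
| 0 | 0.250 | 0.081 | 0.775 |
| 5% | 0.2375 | 0.097 | 0.735 |
| 10% | 0.225 | 0.116 | 0.690 |
| 20% | 0.200 | 0.164 | 0.589 |
| 40% | 0.150 | 0.308 | 0.352 |

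Across the same range of g (0 to 40%), P(stop) rises from 0.164 to 0.434 at a true rate of 20%, and from 0.038 to 0.213 at 30%.

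**The case against.** **The comma in the CRi row could mean 'or'.** This does not hold. The same comma in the CR row can only mean 'and', and Table 4 in Section 6.2 writes 'or' where either count suffices. An 'or' reading would also make every CRp patient a CRi patient. Section 11.1.1 names CRi but not CRp, so that reading would change the count too. The row needs an edit either way.

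**The patient is not without any category.** A reader might infer that Table 6 gives this patient nothing at all. That is too strong. HI has no blast condition, and a platelet rise from 50,000 to 100,000 or more is major HI. SD is available in Parts 2 to 4. Only a Part 1 patient without HI has no category.

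**The reach is limited.** A reader might also infer that all four parts are distorted. They are not. Clinical benefit in Parts 2 to 4 omits CRi, and complete response in Part 2 is CR or CRp, so a CRi patient gains nothing there over the gap patient. The screening rule excludes the MDS stratum, whose expansion trigger uses CR, CRp, PR and major HI.

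**Some looks may be past.** Section 3.3 reports on 60 patients in the original AML cohort, which equals three arms at the screening maximum of 20. Section 3.4 plans about 100 AML patients in Part 1. No arm-level accrual is given, but the stopping looks may already have been taken. This stands as a limit on the futility figures. The reported CRi rate and the 20% condition still rest on Table 6.

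**The state may be temporary.** Under Table 4, study drug is held with blasts ≤5% and a low count, and such a patient may later qualify as CR. This stands as a reason why g may be small. It does not make g zero, and a look could fall before neutrophils recover.

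**Conclusion.** The gap is real, and it matters for the Part 1 AML rules and the reported CRi rate. Followed literally, Table 6 makes a marrow remission with isolated neutropenia a non-response while a remission with both counts low is counted.

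The size cannot be fixed from the documents. At a true rate of 25%, the added stopping probability is 0.016 if 5% of responders fall in the gap (0.097 − 0.081) and 0.227 if 40% do (0.308 − 0.081). These figures assume independent patients and looks at exactly 10 and 17.

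The documents do not support reading this as a flaw in a primary endpoint. One-year survival, the primary endpoint of Parts 1, 3 and 4, does not use Table 6, and the Part 2 co-primary endpoints give CRi no credit. Nor does 4 of 20 guarantee expansion, because Section 11.1.1 makes it optional and conditional on 30-day deaths. This is a minor definitional correction.

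A related ordering problem lies beside it. The rules name CR and CRi only, so a CRp patient, whose neutrophils have recovered, is also uncounted while a patient with both counts low is counted.

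**What to change.** In Table 6, define CRi as blasts ≤5% with neutrophils <1000 and/or platelets <100,000, not meeting CRp, with the other conditions unchanged. All four count combinations with blasts ≤5% are then assigned exactly once, and Table 8 again applies at the true rate (0.081 at 25%).

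In Sections 11.1.1 and 11.4, state whether CRp counts within CR plus CRi. Widening CRi alone would leave the CRp ordering problem in place.

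The wording change is a short phrase and needs no new data, because blasts, neutrophils and platelets are already collected. It does need a protocol amendment and reclassification of enrolled patients. Part 1 response data have already been seen (Section 3.3), so this would be a data-informed change to a response definition. Apply the revised definition to all Part 1 patients, and report the CRi rate under both the present and the revised definitions.

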### 1.5. Rationale for a Phase II Study in Elderly Patients with AML or MDS

Nucleoside analogues play an important role in the treatment of leukemias and myelodysplastic syndromes (MDS). Ara-C and fludarabine, both nucleoside analogues, are the two most active drugs in these diseases. Despite the impressive ability of these agents to induce partial or complete responses, leukemias and MDS remain incurable in many patients, especially the elderly. This is because responses are usually not durable and the treatment carries significant toxicities. New effective drugs are required to improve the outcome of these diseases.

Sapacitabine, a rationally designed nucleoside analogue, has a unique mechanism of action and good oral bioavailability. In preclinical studies, it demonstrated significant activity against a wide range of malignancies. In the mouse P388 leukemia model, mice treated with sapacitabine had a survival advantage when compared with mice treated with 5'-DFUR.

In the phase I trial of sapacitabine in advanced leukemias or myelodysplastic syndromes (CYC682-05-04), sapacitabine had a favourable safety profile and promising anti-leukemic activity in patients with relapsed and refractory AML and MDS when administered by two different dosing schedules. The MTD was reached at 375 mg on the 7-day schedule and 475 mg on the 3-day schedule. Among 42 patients with AML, the best responses were complete remissions (CR) or complete remissions without platelet recovery (CRp) in 5 patients (age 58, 59, 66, 82, 86) who have relapsed and/or refractory disease following prior therapies consisting of ara-C, anthracycline, clofarabine, mylotarg, fludarabine and/or bone marrow transplant. In addition, 13 patients had a significant decrease in bone marrow blasts including 5 with blast reduction to 5% or less. Among 3 patients with MDS, the best responses were complete remissions (CR) in 1 patient (age 79) and the other 2 patients (age 75, 73) had a decrease of bone marrow blasts to 5% or less. All 3 MDS patients had failed a prior therapy with azacitidine or decitabine.

The rationale for conducting this study in elderly patients with AML or MDS is to assess the efficacy and safety of 3 dosing schedules in this patient population and to select a better dosing schedule for further clinical development.

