Arm I	100 mg q.d. x 5 consecutive days per week for 2 weeks every 4 weeks	50 mg q.d. x 5 consecutive days per week for 2 weeks every 4 weeks	50 mg q.d. x 5 consecutive days every 4 weeks

Patients who had treatment delay > 2 weeks due to drug-related non-hematologic toxicities will also have dose reductions according to Table 3.

Dose reduction for drug-related toxicities may be undertaken temporarily or permanently for individual patients to ensure safety according to the assessment and judgment of the investigator in the following situations:

- Decrease dose by 50 mg b.i.d. (Arm A, B, C, D, F, G and Part 2) or 50 mg q.d.(Arm E, H, I) for grade 2 toxicity in a frail patient (See Appendix D)
- Decrease dose by 100 mg b.i.d. (Arm A, B, C, D, F, G and Part 2), or 100 mg q.d. (Arm E, H) or 50 mg q.d. (Arm I) for  $\geq$  grade 3 toxicity in a frail patient or a patient who has experienced more than one  $\geq$  grade 3 drug-related toxicity.

Decisions on treatment delay and dose modifications for drug-related hematologic toxicities should be guided by findings from bone marrow biopsy and/or aspirate as well as time to absolute neutrophil count (ANC) and platelet count recovery according to Table 4. Deviations from the guidelines are permitted to ensure safety and serve the best interest of the patient according to the assessment and judgment of the investigator. The reason for deviating from the guidelines should be documented in source documents.

Table 4 Guidelines on Treatment Delay and Dose Reduction for Hematologic Toxicities

Finding from bone marrow biopsy/aspirate	ANC ≥1000 and platelet count ≥100,000 by or on Day 28 of the cycle	ANC < 1000 or platelet count <100,000 on or after Day 28 of the cycle
Blasts are less than or equal to 5%	Administer study drug;  Decrease dose by 50 mg b.i.d* or 50 mg q.d.** for clinically significant and drug-related hematologic toxicity during the previous cycle	Hold study drug and repeat bone marrow when ANC and platelet count recover to baseline or better; if bone marrow blasts remains at 5% or less, continue to hold the study drug until ANC $\geq$ 1000 and platelets $\geq$ 100, 000 or until bone marrow blasts are increasing to $>$ 5%, whichever comes first; decrease by 100 mg $b$ , $i$ . $d$ * or 100 mg $q$ . $d$ .** for delay in ANC and platelet count recovery to the best level on study beyond Day 42

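### CRi counts toward the Part 1 AML futility and expansion rules, yet beyond short transfusion independence it has no cellularity, minimum-count or confirmation condition

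*Combined protocol and SAP*

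**What the plan says.** **Definition.** Section 9, Table 6 gives the marrow and count criteria for CRi as "Normalization of bone marrow to $\leq$ 5% blasts; peripheral neutrophils $<1000~/\mu$ L, platelet $<100,000/\mu$ L within 2 weeks of bone marrow biopsy/aspirate". The row then adds the condition that CR and CRp also carry, "independent of transfusions*; and no extramedullary leukemia". The table footnote defines transfusion independence as "no packed red blood cell transfusion for 2 weeks and no platelet transfusion for 1 week". Neither Section 9 nor any other section mentions cellularity, sample adequacy, a minimum or rising count, a confirmatory marrow or a minimum duration. Duration of response "is measured from the time when response criteria are first met until the first date that recurrent or progressive disease is documented". Central review is optional, and under Section 3.7 the investigator's case report form pages may serve as source data for response.

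**Timing.** Table 5, footnote h, says of the on-study marrow: "To be performed prior to the start of cycle 2 on patients who have >5% blasts in bone marrow". It falls at Day 21 to 28 of Cycle 1 and may be put off to Day 35 for count recovery. Later marrows are done as clinically indicated.

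**Use.** Section 11.1.1 stops an AML arm at 0 of 10 or 1 of 17 with CR or CRi. At the first look: "If at least one CR or CRi is observed, add AML patients to reach a total of 17 patients". An arm with at least 4 CR and CRi may be expanded if its 30-day death rate is 20% or less. Section 11.4 analyses separately the additional patients on a schedule with at least 20% CR/CRi.

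**Dosing guideline.** For blasts of 5% or less with low counts at Day 28 or later, Section 6.2, Table 4 says: "Hold study drug and repeat bone marrow when ANC and platelet count recover to baseline or better".

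**The concern.** A low blast percentage in a nearly empty marrow can reflect drug effect on all cells and need not mean remission. Section 1.6 lists myelosuppression among the major expected toxicities, and the first on-study marrow comes three to five weeks after the start of a cytotoxic drug.

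Consider a hypothetical record: a hypocellular marrow on Day 24 with 3% blasts, neutrophils 300, platelets 40,000, no red cells for 2 weeks and no platelets for 1 week. Without extramedullary disease, every Table 6 condition for CRi is met. If the repeat marrow shows 30% blasts, nothing in the plan withdraws the CRi; it only ends its duration.

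The activity screen for the Part 1 AML arms rests on CR plus CRi alone. An evaluable patient need have completed only one cycle, so this first marrow can decide the 10-patient look. At stake is whether an insufficiently active schedule passes the screen and becomes a candidate for expansion.

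**Working it through.** **1. Table 6 beside Table 4.** For the same finding (blasts at or below 5%, low counts), Table 4 treats the marrow as provisional: it asks for a repeat and acts on whether blasts stay at 5% or less. Table 6 treats it as final. Section 9 also asks for a second assessment before recurrence or progression is accepted in a possible temporary flare, but has no counterpart for a temporary clearance of blasts.

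**2. Reproducing the plan's boundaries.** Inputs from Section 11.1.1: beta(1,1) prior, stop if P(rate > 25% | data) < 0.05, at most 20 patients per arm.
- 0 of 10: 0.75^11 = 0.042. This is the first sample size at which zero responses trigger a stop.
- 1 of 17: 0.75^18 + 18 × 0.25 × 0.75^17 = 0.0395. This is the first sample size at which one response triggers a stop.

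**3. Reproducing Table 8.** For scored rate p:

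P(stop) = (1 − p)^10 + 10p(1 − p)^9 × (1 − p)^7 = (1 − p)^10 + 10p(1 − p)^16

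| p | Table 8 | Exact |
|---|---|---|
| 0.05 | 0.822 | 0.819 |
| 0.10 | 0.54 | 0.534 |
| 0.15 | 0.313 | 0.308 |
| 0.20 | 0.165 | 0.164 |
| 0.25 | 0.082 | 0.081 |
| 0.30 | 0.039 | 0.038 |

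The largest gap is 0.006. Table 8 is correct for the rate as scored.

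**4. Sensitivity to misclassification (assumption).** Let t be the true CR plus CRi rate and q the share of non-responders scored as CRi only because of a transient hypocellular marrow. The scored rate is then p = t + (1 − t)q. The documents give no value for q, so 0 to 20% is shown.

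Example, t = 0.05 and q = 0.10: p = 0.05 + 0.95 × 0.10 = 0.145, and P(stop) = 0.855^10 + 1.45 × 0.855^16 = 0.209 + 0.118 = 0.327.

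| q | t = 5%: P(stop) | t = 5%: P(pass and ≥4 of 20) | t = 10%: P(stop) | t = 10%: P(pass and ≥4 of 20) |
|---|---|---|---|---|
| 0% | 0.819 | 0.015 | 0.534 | 0.128 |
| 5% | 0.547 | 0.120 | 0.327 | 0.318 |
| 10% | 0.327 | 0.318 | 0.187 | 0.531 |
| 15% | 0.181 | 0.542 | 0.101 | 0.713 |
| 20% | 0.094 | 0.730 | 0.052 | 0.842 |

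The columns for passing with at least 4 of 20 are exact binomial path probabilities. They do not model the 30-day death condition on expansion, so they are not probabilities of expansion.

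**The case against.** Several points on the other side stand.

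- A reader might infer that CRi has no recovery condition at all. That is wrong: a patient in deep aplasia who is being transfused cannot be scored CRi. The safeguard is short, though, and sets no floor for neutrophils or cellularity.
- Footnote h lets the first marrow wait until Day 35 for count recovery, which reduces the problem. It does not require waiting.
- A reader might size the problem from the phase I results in Section 1.5, where 5 of 42 AML patients had CR or CRp and a further "13 patients had a significant decrease in bone marrow blasts including 5 with blast reduction to 5% or less". Those data do not measure aplasia. Nothing says that any of these marrows was hypocellular, any of the five could be a genuine CRi, and the baseline counts CR/CRp whereas the rule counts CR and CRi.
- A reader might infer that the choice of schedule is tilted toward the more myelosuppressive arms. The documents do not show this. Section 11.1.2 selects on 1-year survival among schedules with similar toxicity, and Section 11.1.1 has a separate toxicity stop.
- Expansion is optional and needs a 30-day death rate of 20% or less. The 20% rule only governs separate analysis. Parts 2, 3 and 4 and the MDS expansion rule do not use CRi.
- Section 3.3 already reports results from a first AML cohort of 60 patients, about 20 per arm at 1:1:1, so the 10- and 17-patient looks appear to be over. Re-scoring now, in an open-label study with results known, carries its own risk of bias. This shapes the fix but does not remove the gap.
- The CRi row cites published response criteria that are not part of the documents. Any marrow-adequacy condition there is not stated in this plan.

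**Conclusion.** The point holds in a limited form. As written, Table 6 allows a transient, transfusion-free hypocellular marrow to count as CRi, and that CRi feeds the Part 1 AML futility stops, the expansion count and the 20% separate-analysis rule. Table 4 already treats the same finding as provisional.

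The size is unknown, because the documents give no misclassification rate. Under the assumption of a 5% true rate with 10% of non-responders scored this way, the stop probability falls from 0.82 to 0.33, and the chance of passing futility with at least 4 of 20 rises from 0.015 to 0.32. If no such marrow is scored, nothing changes.

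The effect is confined to the activity screen, the expansion count and the CRi secondary endpoint. The primary endpoint, 1-year survival, is not affected. This is an inexpensive improvement to the scoring and does not show that the Part 1 design fails.

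**What to change.** Change the scoring only; dosing and the schedule of procedures stay as they are.

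- In Table 6 and Section 11.1.1, count a CRi whose marrow is reported as aplastic or hypocellular only if a later marrow, such as the repeat already called for in Table 4, still shows 5% blasts or less. Date the confirmed CRi from the first qualifying marrow.
- Because the first AML cohort appears already evaluated and the study is open label, report CR plus CRi under Table 6 as written and under the confirmed definition, side by side. Do not replace the count already used. State how many CRi calls could not be confirmed, and why.

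Cost: a sentence in each of the two places and one extra line in the response table. The confirmed CRi count will be slightly lower, and some calls will come later. Some marrows will be unconfirmable: Table 5 allows an aspirate without a biopsy, so cellularity may not have been reported, and Table 4 permits deviations and ties the repeat to count recovery, so it may not have been done.
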